## 2.3.4 Safety and clinical activity

The overall safety experience with nivolumab, as a monotherapy or in combination with other therapeutics, is based on experience in approximately 20,200 subjects treated to date. For monotherapy, the safety profile is similar across tumor types. In Phase 3 controlled studies, the safety profile of nivolumab monotherapy is acceptable in the context of the observed clinical efficacy, and manageable using established safety guidelines. Clinically relevant AEs typical of stimulation of the immune system were infrequent and manageable by delaying or stopping nivolumab treatment and timely immunosuppressive therapy or other supportive care.

Two studies evaluated the efficacy of nivolumab as a single agent in adult patients with cHL after failure of autologous stem cell transplantation (ASCT). CHECKMATE-205 (NCT02181738) was a single-arm, open-label, multicenter, multicohort trial in cHL. CHECKMATE-039 (NCT01592370) was an open-label, multicenter, dose escalation trial that included patients with cHL. Patients received nivolumab 3 mg/kg by intravenous infusion every 2 weeks until disease progression, maximal clinical benefit, or unacceptable toxicity. Efficacy was evaluated in 258 patients in CHECKMATE-205 and CHECKMATE-039 combined who had relapsed or progressive cHL after ASCT. Patients had a median of 4 prior systemic regimens (range: 2 to 15), with 85% having 3 or more prior systemic regimens and 76% having prior brentuximab vedotin. Patients received a median of 21 doses of nivolumab (range: 1 to 48) and achieved a best ORR of 69% and a CRR of 14%. The median PFS was 13.1 months. The median DOR has not yet been reached. In the larger phase II CHECKMATE-205 study, the most common drug-related adverse events were fatigue (23%), diarrhea (15%), infusion relation (14%), rash (12%), nausea (10%), and pruritus (10%). Grade 3 or higher drug-related adverse events occurring in at least 1% of patients included: lipase increase (5%), neutropenia (3%), ALT increase (3%), AST increase (2%), amylase increase (2%), pneumonia (1%)(3,8).

## 2.3.5 Safety of combination ipilimumab and nivolumab

The combination of nivolumab + ipilimumab is approved in subjects with unresectable or metastatic melanoma as well as metastatic renal cell carcinoma and is currently being studied in multiple tumors. Results to date suggest that the safety profile of nivolumab + ipilimumab combination therapy is consistent with the mechanisms of action of nivolumab and ipilimumab. The nature of the AEs is similar to that observed with either agent used as monotherapy; however, both frequency and severity of most AEs are increased with the combination.

The combination of nivolumab (3 mg/kg) plus ipilimumab (1 mg/kg) was tested in 550 patients with advanced stage renal cell carcinoma as part of a phase III trial. In this cohort, the most common treatment-related adverse events were fatigue (37%), pruritus (28%), diarrhea (27%), rash (22%), nausea (20%), increased lipase level (16%), decreased appetite (14%), asthenia (13%), and vomiting (11%). Grade 3 or higher drug-related adverse events occurring in at least 1% of patients included: increased lipase (10%), diarrhea (4%), fatigue (4%), rash (1%), nausea (1%), decreased appetite (1%), and asthenia (1%)(9). This combination was also tested in 31 patients with cHL as part of a phase 1b trial in 65 patients with relapsed hematologic malignancies. In this cohort, the most frequent adverse events were fatigue (26%), pyrexia (23%), and diarrhea (18%). In total, 19 pts (29%) had a drug-related AE of grade ≥3(10).

#### 2.4 Rationale

Classic Hodgkin lymphoma (cHL) is characterized by an unusual tissue architecture composed of rare Reed-Sternberg (RS) cells surrounded by a complex network of immune cells that are unable to mount an effective anti-tumor immune response. In recent years, investigators have uncovered mechanisms by which RS cells evade immune detection, which has enabled significant therapeutic breakthroughs in cHL. Nearly all patients with cHL harbor genetic alterations in 9p24.1, an amplicon which contains the genes for both PD-1 ligands, PD-L1 and PD-L2(11). The amplicon also contains the JAK2 gene and augmented JAK/STAT signaling generates additional production of PD-L1 and PD-L2 proteins. Together, these alterations drive abundant expression of PD-1 ligands on RS cells which can bind to PD-1 on infiltrating effector immune cells leading to inactivation and immune evasion. Based on this genetic dependency, patients with cHL were included as independent cohort expansions in phase I trials of PD-1 inhibitors. These and subsequent phase II trials reported overall response rates (ORRs) of around 70% which led to the FDA approval of two PD-1 inhibitors, nivolumab and pembrolizumab, for relapsed/refractory (R/R) cHL(3,4,8,12).

However, even with the success of PD-1 directed mAb in cHL, significant challenges remain for patients with R/R disease. Approximately 10-15% of patients will progress rapidly with PD-1 blockade and many other patients will experience limited disease control with these agents(3,4). In particular, patients who achieve a best response of stable disease or partial response (~70% of all patients) achieve more limited progression-free survival (PFS) (11.2 months and 15.1 months, respectively) compared to patients who achieve a complete response (22.2 months)(3). Novel treatment strategies are needed for patients who achieve an incomplete response or who experience progression on PD-1 blockade.

While alterations in the PD-1 signaling axis are nearly universal and appear to be critical for cHL pathogenesis, numerous other immune checkpoint receptors and ligands are present in the cHL tumor microenvironment (TME) and may also play important roles in immune evasion. These immune checkpoints offer additional potential targets for therapeutic intervention. Patel et al. used multiplex immunofluorescence to analyze the expression and distribution of the inhibitory immune checkpoint receptor CTLA-4 and its ligand CD86 in cHL. They found frequent expression of CTLA-4 on intratumoral T cells and strong expression of CD86 on nearly all RS cells as well as on a subset of tumor-associated macrophages (TAMs). Intratumoral T cells were more likely to express CTLA-4 than PD-1 and both CTLA-4 and CD86 were enriched within PD-L1 positive clusters of RS cells and TAMS, suggesting that CTLA-4 may also be important for maintaining an immunosuppressive niche for RS cells. Importantly, frequent CTLA-4 and CD86 expression in the cHL TME was seen both before and after treatment with PD-1 blockade(13).

These results provide a strong scientific rationale for additional clinical investigation of CTLA-4 directed therapies in cHL. Already, there are several small studies that suggest that ipilimumab has clinical activity among patients with R/R cHL. Two trials have investigated single-agent ipilimumab among patients with relapsed disease after allogeneic transplantation. Two of fourteen patients achieved a complete response (CR) after a single dose of ipilimumab in an initial study(14), and 4 of 7 patients achieved a reduction in tumor burden (including 1 partial

response) in a subsequent study that employed repeated dosing of ipilimumab(15). Despite its use after allogeneic transplantation (where the risk of immune-related complications including graft-versus-host disease is high), the safety profile of single agent ipilimumab was manageable. The largest experience with CTLA-4 blockade in cHL comes from a trial combining ipilimumab (1 mg/kg) with nivolumab (3mg/kg) in patients with R/R hematologic malignancies. In this trial, 31 patients with HL received 4 cycles of combination therapy followed by nivolumab monotherapy every 2 weeks for up to 2 years. Response rates with the combination (ORR 74%, CRR 19%) were similar to PD-1 blockade monotherapy, but longer-term follow-up suggests that combination therapy may be associated with more durable remissions(10). The 18-month PFS with combination ipilimumab and nivolumab (~65%) which compares favorably to that observed with nivolumab monotherapy in the phase II CHECKMATE 205 trial (median PFS of 14.7 months). Higher rates of immune-related adverse events (irAEs) were observed with ipilimumab and nivolumab compared to nivolumab monotherapy, however, most irAEs were manageable. The rate of treatment discontinuation due to adverse events with combination therapy was similar to that observed in phase II trials of PD-1 mAb monotherapy (8% vs 4-6%)(3,4,10). Ipilimumab (1 mg/kg every 12 weeks) has also been tested in R/R cHL as part of a triplet therapy with nivolumab (3mg/kg every 3 weeks) and BV (1.8 mg/kg every 3 weeks). Among 22 patients, the ORR and CRR were 82% and 72%, respectively. Frequent adverse events were observed and while these were typically manageable, 3 patients (14%) discontinued therapy after one cycle(16).

The frequent expression of CTLA-4 and its ligand CD86 within the cHL TME provide a strong biologic rationale for CTLA-4 directed therapies in cHL. In addition, available clinical data suggests that ipilimumab has clinical activity and a tolerable risk profile when used as monotherapy or in combination with nivolumab. We have designed a phase II trial that targets the use of ipilimumab to those patients who derive less benefit from PD-1 blockade with the goal of limiting overall toxicity exposure. The trial will utilize a response-adapted design among patients who failed PD-1 mAb therapy. Patients will begin with ipilimumab monotherapy and then undergo a restaging PET/CT. Patients achieving an objective response will continue treatment with ipilimumab maintenance, while non-responders will receive ipilimumab and nivolumab re-induction therapy for 4 cycles followed by ipilimumab maintenance treatment. Given the key role of the PD-1 axis, we hypothesize that some patients may benefit from the addition of nivolumab to CTLA-4 blockade even after they have progressed following treatment with both treatments alone. Observation of objective responses to combination therapy with nivolumab and ipilimumab in this setting would provide strong evidence of synergy with combined PD-1 and CTLA-4 blockade.

### 2.5 Correlative Studies Background

### 2.5.1 Multiplex immunofluorescence (MIF):

This study will incorporate a laboratory technique known as MIF, which is used to examine the expression and distribution of up to 6 antigens of interest within formalin-fixed paraffin embedded (FFPE) tissue. The technique allows for examination of co-localization of proteins of interest and protein-protein interaction. MIF has been used successfully to interrogate the TME of multiple subtypes of lymphoma, including Hodgkin lymphoma, where it clarified the critical

roles of the PD-1 and CTLA-4 in maintaining an immunosuppressive microenvironment(13,17). We aim to use MIF to characterize the expression of immune checkpoint proteins (CTLA-4, CD86, PD-1, PD-L1, and others) and to describe the distribution of immune cells, including CD8+ T cells, CD4+ T cells, T regulatory cells, NK cells, and tumor-associated macrophages (TAMs). In addition, using on-treatment and post-progression tumor samples we will describe alterations following treatment with ipilimumab +/- nivolumab. We hypothesize that there may be baseline TME features that predicts response to ipilimumab +/- nivolumab therapy. In addition, post-progression biopsies may suggest mechanisms of resistance that could be explored further in subsequent studies.

### 2.5.2 Multiplex Ion Beam Imaging (MIBI):

Simultaneous detection of multiple targets is limited by spectral overlap of the fluorophores used to tag individual antibodies. Due to this technical limitation, MIF typically cannot assess more than 6 antigens at a time. Multiplex Ion Beam Imaging (MIBI) uses secondary ion mass spectrometry to image antibodies carrying metal isotopes. As a result, MIBI is capable of analyzing samples stained simultaneously with more than 40 metal-isotope labelled antibodies(18). This technique will be used in conjunction with MIF to analyze the TME of cHL, characterize the expression of immune checkpoint proteins, and describe the distribution of immune cells. In addition, using on-treatment and post-progression tumor samples we will describe alterations following treatment with ipilimumab +/- nivolumab.

## 2.5.3 Circulating tumor DNA (ctDNA):

Plasma is a source of circulating tumor DNA (ctDNA) which can be used for to identify tumor genotypes, copy number abnormalities, immunoglobulin gene rearrangements, and single gene mutations. In addition, serially collected plasma samples can be used to track the level of ctDNA over time in response to therapy. In multiple tumor lymphoma subtypes, including diffuse large B-cell lymphoma (DLBCL) and cHL, an early drop in level of ctDNA (i.e. 2 log reduction) after 2 cycles of induction chemotherapy has been associated with a significant improvement in PFS(19,20). Early data suggests that changes in levels of ctDNA may also hold predictive value for patients with lymphoma receiving immune-based therapies(21,22). We plan to collect serial plasma samples for analysis of ctDNA. Our group is currently developing an assay for ctDNA evaluation in cHL. We will quantify circulating tumor DNA at different timepoints and analyze changes in copy number abnormalities and relevant pathogenic gene. We hypothesize that an early reduction in ctDNA will be associated with clinical response and improved PFS. We will also use serial samples to characterize the genetic bases of immune evasion and correlate these alterations with responses to therapy

Protocol version date: v8/06 September 2023

#### 3. PARTICIPANT SELECTION

## 3.1 Eligibility Criteria

Participants must meet the following criteria on screening examination to be eligible to participate in the study:

- 3.1.1 Patients must have histologically determined classic Hodgkin lymphoma with pathologic review at the participating institution.
- 3.1.2 Participants must have measurable disease, defined as a lymph node or tumor mass ≥1.5 cm in at least one dimension by CT, PET/CT, or MR. Imaging must have been completed no greater than 6 weeks prior to study enrollment. Measurable disease that has previously been irradiated is permissible only if there has been evidence of progression since the radiation.
- 3.1.3 Patients must have progressed after two or more lines of systemic treatment, including autologous stem cell transplantation, if eligible.
- 3.1.4 Progression of disease or relapse following treatment with nivolumab or pembrolizumab. Intervening treatments with between PD-1 mAb therapy and the trial are permitted.
- 3.1.5 Patients may have had a prior autologous stem cell transplant and may have been treated with chimeric antigen receptor T-cells (CAR T-cells).
- 3.1.6 Age  $\geq$ 18 years.
- 3.1.7 Eastern Cooperative Oncology Group (ECOG) performance status 0-2 (see Appendix A)
- 3.1.8 Adequate hematologic and organ function as defined below:
  - Absolute neutrophil count >  $1.0 \times 10^9$ /L unless due to marrow involvement by lymphoma in which case ANC must be >0.75x10^9/L. Growth factor support is allowed provided it is received at least 5 days prior to enrollment labs.
  - Platelets > 75  $\times$  10^9/L, unless due to marrow involvement by lymphoma, in which case platelets must be >50  $\times$  10^9/L
  - Estimated GFR (by Cockroft-Gault equation) > 40ml/min
  - Total bilirubin < 1.5 X ULN
  - AST/ALT < 2.5 X ULN
- 3.1.9 Ability to understand and the willingness to sign a written informed consent document.
- 3.1.10 Willingness to provide pre-treatment tumor sample by core needle or excisional surgical biopsy. An archival sample is acceptable in the following situations: the sample was acquired within 90 days of initiation of PD-1 therapy AND the following provisions are met: 1) availability of a tumor-containing formalin-fixed, paraffin-embedded (FFPE) tissue block, 2) if the tumor containing FFPE tissue block cannot be provided in total, sections from this block should be provided that are freshly cut and mounted on positively-charged glass slides (SuperFrost Plus are recommended). Preferably, 25 slides should be provided; if not possible, a minimum of 15 slides is required. Exceptions to this criterion may be made with approval of the Study Chair.

DF/HCC Protocol #: 21-204 Protocol version date: v8/06 September 2023

3.1.11 Willingness to use contraception during and after study treatment. Women of child-baring potential (WOCBP) will be instructed to adhere to contraception for a period of 5 months following last dose of nivolumab and 6 months following the last dose of ipilimumab. Men receiving nivolumab and who are sexually active with WOCBP will be instructed to adhere to contraception for a period of 7 months after last dose of nivolumab and 6 months after the last dose of ipilimumab.

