# APPENDIX C RESPONSE CRITERIA FOR LYMPHOMA: LUGANO 2014 AND LYRIC

Criteria	Complete Response (CR)	Partial Response (PR)	Stable Disease (SD)	Progressive disease (PD)
Lugano	PET-CT, score 1, 2, or 3* with or without a residual mass on 5PS†  Or  on CT, target nodes/nodal masses must regress to ≤ 1.5 cm in LDi, and no extralymphatic sites of disease	PET-CT Score 4 or 5 with reduced uptake compared with baseline and residual mass(es) of any size.  Or  On CT ≥ 50% decrease in SPD of up to 6 target measurable nodes and extranodal sites; no increase in non-measured lesions; spleen if enlarged must have regressed by >50% in length beyond normal	Neither CR, PR, nor PD	PET-CT score 4 or 5 with an increase in intensity of uptake from baseline and/or new FDG-avid foci consistent with lymphoma at interim or end-of-treatment assessment.  Or  On CT, an individual node/lesion must be abnormal with:  LDi > 1.5 cm and Increase by ≥ 50% from PPD nadir and An increase in LDi or SDi from nadir 0.5 cm for lesions ≤ 2 cm 1.0 cm for lesions > 2 cm In the setting of splenomegaly, the splenic length must increase by > 50% of the extent of its prior increase beyond baseline (eg, a 15-cm spleen must increase to > 16 cm). If no prior splenomegaly, must increase by at least 2 cm from baseline New or recurrent splenomegaly. New or clear progression of preexisiting nonmeasured lesions. Regrowth of previously resolved lesions. A new node > 1.5 cm in any axis or a new extranodal site > 1.0 cm in any axis; if < 1.0 cm in any axis, its presence must be unequivocal and must be attributable to lymphoma Assessable disease of any size unequivocally attributable to lymphoma  And/Or  New or recurrent involvement of the bone marrow

Criteria	Complete Response	Partial Response	Stable Disease (SD)	Progressive Disease (PD)
	(CR)	(PR)		
LYRIC	Same as Lugano	Same as Lugano	Neither CR, PR, PD,	As with Lugano with the following exceptions:
			nor IR	Indeterminate response (IR)
				IR1: ≥50% increase in SPD in first 12 wks
				IR2: <50% increase in SPD with
				a. New lesion(s), or
				b. ≥50% increase in PPD of a lesion or set of lesions at any time during
				treatment
				IR(3): Increase in FDG uptake without a concomitant increase in lesion
				size meeting criteria for PD

SPD – sum of the product of the diameters; PPD – product of the perpendicular diameters; LDi – longest diameter; SDi – short diameter; 5PS – 5-point scale; IR – immune response

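### Entry requires a lesion of at least 1.5 cm but not an FDG-avid one, so a patient with a non-avid residual mass could enter already meeting PET complete response

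*Combined protocol and SAP*

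**What the plan says.** Section 3.1.2 requires measurable disease, "defined as a lymph node or tumor mass ≥1.5 cm in at least one dimension by CT, PET/CT, or MR". The rule concerns size only. It adds one condition on lesion history: "Measurable disease that has previously been irradiated is permissible only if there has been evidence of progression since the radiation".

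Section 3.1.4 requires "Progression of disease or relapse following treatment with nivolumab or pembrolizumab" and then states: "Intervening treatments with between PD-1 mAb therapy and the trial are permitted". It does not ask for progression after the intervening treatment.

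Appendix C gives CR two limbs joined by an unranked alternative. The PET limb is "PET-CT, score 1, 2, or 3* with or without a residual mass on 5PS". The CT limb is "on CT, target nodes/nodal masses must regress to ≤ 1.5 cm in LDi, and no extralymphatic sites of disease". The PET limb for partial response, by contrast, is explicitly relative to baseline: "Score 4 or 5 with reduced uptake compared with baseline and residual mass(es) of any size".

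Section 10.1 makes a screening PET/CT mandatory, but no PET finding is an entry condition. Section 11.1 uses that scan to choose evaluable index lesions and does not define evaluable. Section 13.1 names best objective response rate (ORR) by Lugano as the primary endpoint. Section 13.3 rejects a 10% ORR if at least 4 of 13 patients respond, with a stated type I error of 0.034 and power of 0.83.

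**The concern.** A response should record something that happened after treatment began. The PET limb of CR describes a state, not a change. That is harmless if every patient starts outside that state, but the entry rule does not ensure this. Take a patient who progressed after a PD-1 antibody and then received another regimen that left a mass of 2 to 3 cm with a score of 2 or 3. The size rule is met, the progression rule is met by the earlier event, and the PET limb of CR is met on the screening scan. Such a patient needs only to stay the same until week 12 to count as a responder to ipilimumab.

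The bias runs upward, on the primary endpoint. One such patient would supply a quarter of the four responses needed to declare activity.

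**Working it through.** **Side by side.** For a non-avid residual mass of at least 1.5 cm after intervening drug or cell therapy:

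| Provision | Does it bar the patient? |
|---|---|
| 3.1.2, size | No: size is met and avidity is not asked for |
| 3.1.2, radiation clause | No: it applies to irradiated lesions only |
| 3.1.3, two or more prior lines | No: earlier progressions can satisfy it |
| 3.1.4, PD-1 failure | No: progression may precede the intervening therapy |
| 3.2.1, 28-day washout | No: it delays entry but does not require regrowth |
| 10.1, screening PET/CT | No: the scan is required, its result is not a criterion |
| Appendix C, PET CR | Already met at score 1 to 3 |

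**The plan's own figure.** Inputs from Section 13.3: n = 13, cut-off 4, ORR 10% against 40%.

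P(X ≥ 4 | 13, 0.10) = 1 − [0.9^13 + 13(0.1)(0.9^12) + 78(0.1^2)(0.9^11) + 286(0.1^3)(0.9^10)] = 1 − [0.2542 + 0.3672 + 0.2448 + 0.0997] = 0.034.

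P(X ≥ 4 | 13, 0.40) = 0.831. Both stated figures reproduce.

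**Effect of baseline CRs.** Suppose k of the 13 already meet CR and all k stay unchanged to week 12. The other 13 − k patients then need only 4 − k responses: P = P(X ≥ 4 − k | 13 − k, 0.10).

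- k = 0: 0.034
- k = 1: 1 − [0.9^12 + 12(0.1)(0.9^11) + 66(0.1^2)(0.9^10)] = 1 − [0.2824 + 0.3766 + 0.2301] = 0.111
- k = 2: 1 − [0.9^11 + 11(0.1)(0.9^10)] = 1 − [0.3138 + 0.3835] = 0.303

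The documents give no value for k; 0 to 2 is an assumption. These are ceilings, because each such patient is taken as certain to remain in CR.

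**Same question as a per-patient chance.** Let q be the assumed chance that an enrolled patient both meets CR at baseline and remains so. The apparent ORR under the null is q + (1 − q)(0.10). The chance of at least 4 of 13 is then 0.058 at q = 2%, 0.107 at q = 5% and 0.223 at q = 10%.

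**Cost of not counting such patients.** If a baseline CR cannot count as a response and the cut-off stays at 4, the remaining patients must supply all four. One patient: P(X ≥ 4 | 12, 0.40) = 0.775, type I error 0.026. Two patients: P(X ≥ 4 | 11, 0.40) = 0.704, type I error 0.019.

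**The case against.** The strongest reply is that the trial enrols relapsed or refractory disease. A patient whose only mass scores 1 to 3 is in remission by the plan's own Appendix C, so enrolling that patient means reading 3.1.2 apart from its purpose. There are practical obstacles too. The notes to Table 7 require pre-treatment tissue from everyone, and Sections 5 and 9 accept archival tissue only if no treatment intervened. A patient in this scenario would therefore normally need a fresh biopsy of the residual mass. Responses are also read centrally (Section 11.1.3).

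Most of this stands as a reason to expect few such patients, but it does not close the gap. Section 3.1.10 asks for willingness to provide tissue, words the archival window differently and allows exceptions by the Study Chair. Sections 5 and 9 seek the biopsy when safely feasible. Central readers apply the same criteria, and a non-avid mass passes any PET confirmation of CR.

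It is also fair to object that these patients have failed several lines, and that new avid disease by week 12 would be scored as progression. That is why 0.111 and 0.303 are ceilings.

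A reader might further infer that any 1.5 cm node can be scored CR on CT without changing. The documents do not support that. The two size limits meet only at exactly 1.5 cm, the CT limb says the node "target nodes/nodal masses must regress to ≤ 1.5 cm in LDi", and extralymphatic disease blocks it. The week-12 assessment is PET/CT for everyone, with CT alone allowed only after CR. This is a minor boundary point.

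**Conclusion.** The gap holds for the PET limb of CR. Eligibility by size alone, intervening treatment without a requirement for later progression, and a CR definition that needs no change from baseline together allow a patient to enter already meeting CR. The other provisions make this uncommon without excluding it.

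The size is conditional. At a true ORR of 10%, the chance of a positive trial rises from 0.034 to at most 0.111 with one such patient and at most 0.303 with two, if they remain unchanged to week 12. The number of patients is assumed.

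Two stronger inferences should not be drawn. The plan's type I error is not miscalculated: 0.034 is right for 13 patients who do not already meet CR at entry. Nor do the documents show that any such patient has been or will be enrolled. The point is worth acting on because the decision turns on four responses and the remedy is cheap.

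**What to change.** Amend Section 3.1.2 to require at least one lesion that is longer than 1.5 cm in longest diameter and FDG-avid (score 4 or 5) on the screening PET/CT. This closes the PET gap and removes the exact-1.5 cm overlap. If all 13 patients meet the amended rule, the stated type I error and power stand.

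For patients already enrolled, have the central imaging core check the stored baseline scans. Prespecify in Section 13.5.2 that a CR already present at baseline is not counted as a response, and report the ORR with and without any such patient. That section now refers only to evaluable patients, without a definition, so handling such a case without a prior rule would be a decision made after the fact.

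Costs: the scan and the imaging core are already in place, so the work is a few lines of text and one review of stored scans. An occasional patient with non-avid or borderline disease would not be enrolled. Not counting a baseline CR lowers power from 0.83 to 0.775 for one patient and 0.704 for two. The analysis plan should state this, because such a patient can then never contribute a response.
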